4.6 Demographic and Baseline Characteristics

Summary tables and listing will be provided as follows for ITT, PPS, PK-PPS and SAF.

Demographics and baseline characteristics will be summarized as collected at screening or baseline visit before administration of first dose of study drug and will include:

- gender,
- race (American Indian/Alaska Native, Asian [Japanese], Asian [Non-Japanese], Black/African American, Native Hawaiian/other Pacific Islander, White and Other),
- geographic region (Asia, Europe/other),
- age (years), Age category(<65, >=65 years)
- ethnicity,
- height,
- body weight (the first and the third quartiles of body weight will be presented),
- body mass index (BMI, kg/m2), BMI category ($<18.5, \ge 18.5$ to $<25, \ge 25$ to <30, and ≥ 30 kg/m2),

TP-GDO-WW-016-01 Confidential Version 7.0 Effective Date: 28Aug13 Version Date: 28NOV2018 Related to: SOP-GDO-WW-019 Page 14 of 60

- Prior therapy for prevention of NMO/NMOSD attack (B-cell depleting therapy or immunosuppressants/others),
- Most recent attack in the last one year prior (first attack or relapse),
- AQP4 status at screening (positive, negative), and
- Diagnosis (NMO, NMOSD) by treatment group and overall.

The following listing will be provided.

• A by-subject listing of demographic data.

Age will be calculated as the number of complete years between a subject's birth date and the date of the first informed consent.

4.7 Medical History

Medical history will be classified according to the terminology of the latest version of the Medical Dictionary for Regulatory Activities (MedDRA).

Medical conditions are categorized as past or baseline as follows:

- Past diseases: Medical conditions which are specified as start date is before Day 1 Visit date with no ongoing status or the stop date is prior to Day 1 Visit date.
- Baseline diseases: Medical conditions which are specified as start date is before Day 1 Visit date with ongoing status or with the stop date on or after Day 1 Visit date.

The following summaries will be provided by treatment group and overall, based on the SAF.

- A summary table of past diseases will be provided by system organ class (SOC) and preferred term (PT), by treatment group and overall.
- A summary table of baseline diseases will be presented by SOC and PT, by treatment group and overall.
- A by-subject listing of medical history data will be provided.

4.8 Prior and Concomitant Medications

Prior and concomitant medications will be coded using the World Health Organization Drug Dictionary (WHO-DD).

Medication start and stop dates will be compared to the date of the first dose of randomized study drug and thus the medications will be classified as Prior and / or Concomitant.

Medications that start and stop prior to the date of first dose of study drug will be classified as Prior medications. Medications taken on or after (including ongoing) the first dose of study drug will be classified as Concomitant medication. If a medication starts before the date of first dose of study medication and stops on or after the date of first dose of study medication then the medication will be classified as both Prior and Concomitant medication. NMO/NMOSD pain drugs will be reported as collected on the CRF.

TP-GDO-WW-016-01 Confidential Version 7.0 Effective Date: 28Aug13 Version Date: 28NOV2018

Related to: SOP-GDO-WW-019 Page 15 of 60

- A summary table of Prior Medications (other treatments than NMO/NMOSD) will be provided by anatomical therapeutic chemical (ATC) and PT.
- A summary table of Concomitant Medications (other treatments than NMO/NMOSD) will be provided by ATC and PT.
- A summary table of Prior NMO/NMOSD drugs for relapse prevention will be provided by ATC and PT.
- A summary table of Concomitant NMO/NMOSD drugs for relapse prevention will be provided by ATC and PT.
- A summary table of Prior NMO/NMOSD drugs for relapse/rescue therapy will be provided by ATC and PT.
- A summary table of Concomitant NMO/NMOSD drugs for relapse/rescue therapy will be provided by ATC and PT.
- A summary table of Prior NMO/NMOSD pain drugs will be provided by ATC and PT.
- A summary table of Concomitant NMO/NMOSD pain drugs will be provided by ATC and PT.
- A summary table of Prior other NMO/NMOSD drugs will be provided by ATC and PT.
- A summary table of Concomitant other NMO/NMOSD drugs will be provided by ATC and PT.
- A by-subject listing of Prior medication data will be provided for NMO/NMOSD
- A by-subject listing of Concomitant medication for NMO/NMOSD.

4.9 Treatment Compliance

Overall compliance will be assessed for each subject. Compliance will be computed by determining the number of SC injections relative to the number of SC injections that should have been administered. The compliance will only be evaluated during the double-blind period. For subjects who experience a protocol-defined relapse which is confirmed by CEC or discontinued from study treatment early, the number of planned and actual SC injections will be counted based on the visits before the discontinuation. Treatment compliance will be summarized in terms of compliance based on the Safety population.

Compliance will be calculated using the following formula:

Compliance (%) =
$$\frac{\text{Number of SC injections during the double-blind period}}{\text{Number of planned SC injections during the double-blind period}} \times 100$$

The following summaries and listings will be provided:

• A summary table of compliance will be presented by treatment group, and overall. The number and percentage of treatment compliance will also be presented by categorized compliance as: <80%, 80%-100%, >100%.

TP-GDO-WW-016-01 Confidential Version 7.0 Effective Date: 28Aug13 Version Date: 28NOV2018

Related to: SOP-GDO-WW-019

Page 16 of 60

 A by-subject listing of study drug administration as well as overall compliance during study duration of the double blind and study duration of the SA237 exposure

4.10 Efficacy Evaluation

For the definition of the double-blind period for efficacy evaluations see section 4.2. See Appendix 7.1 how to describe models with SAS code.

4.10.1 Analysis and Data Conventions

This study is designed to assess the efficacy of SA237 over placebo in the treatment of NMO/NMOSD. The null hypothesis for primary endpoint will be that there is no difference on the TFR between SA237 monotherapy and placebo during the double-blind period. The alternative hypothesis will be that there is a difference in TFR during double-blinded period.

A two-sided stratified log-rank test at 5% level will be used to test this hypothesis.

4.10.1.1 Multi-center Studies

For the purpose of the summaries and analyses, the term 'Center' will be used to define each site.

All centers will be pooled for the purpose of analysis.

Descriptive summaries will not be presented by individual center. Patient data listing will be provided by individual center.

4.10.1.2 Adjustments for Covariates

The primary efficacy analysis will be adjusted for the following baseline covariates:

- Prior therapy for prevention of NMO/NMOSD attack (B-cell depleting therapy or immunosuppressants/others)
- Most recent attack in the last one year prior to screening (first attack or relapse).

For each covariate, a statistical test for the presence of a treatment-by-covariate (i.e. stratification factors) interaction will be performed, by including the interaction term in the secondary analysis model. Subgroup analyses will be performed to further explore the treatment-by-covariate interactions. If any of the treatment-by-covariate are found to be statistically significant, conclusions based on the secondary analysis (no interaction) will be interpreted with caution.

In addition, the ANCOVA and the Mixed-effect model repeated measures (MMRM) for secondary endpoints will be adjusted for prior therapy for prevention of NMO/NMOSD attack and most recent attack in the last one year prior to baseline (stratification factors).

4.10.1.3 Handling of Dropouts or Missing Data

TP-GDO-WW-016-01 Confidential Version 7.0 Effective Date: 28Aug13 Version Date: 28NOV2018

For details on censoring rule for the primary endpoint, see section 4.10.2 and handling of missing data for the key secondary efficacy endpoints see section 4.10.3.

For secondary continuous endpoints, a Mixed-effects model repeated measures analysis incorporating all data in double blind period will be used to utilize all the data collected over time with consideration of the variance-covariance matrix of the repeated measures. This method allows a general unstructured variance-covariance matrix and will include data from patients with incomplete data from some scheduled time points.

For FACIT fatigue questionnaire, if there are less than 7 responses recorded, then the total fatigue score will be considered missing. If there are 7 or more responses recorded, then the total fatigue score for that questionnaire will be calculated as the average of the non-missing scores multiplied by 13.

4.10.1.4 Multiple Comparisons/Multiplicity

The serial gatekeeping methodology will be employed to control the rate of false positive for the primary endpoint (TFR based on CEC confirmed protocol-defined relapses) and key secondary endpoints (change in VAS for pain to Week 24 and change in the FACIT fatigue scale to Week 24). The 3 efficacy endpoints will be analyzed in hierarchical order, beginning with the TFR based on protocol-defined relapses, followed by the VAS for pain, and ending with FACIT fatigue. A fixed-sequence approach will be applied to control the overall significance level at 0.05. An initial null hypothesis will be tested for the first hierarchical primary efficacy endpoint, the TFR based on protocol-defined relapses. If this is significant, then a repeat of the aforementioned testing procedure for the second hierarchical key secondary endpoint, the VAS for pain will be done. This will be repeated a third time for the FACIT fatigue if the VAS for pain showed a significant difference.

4.10.1.5 Examination of Subgroups

The primary and key secondary endpoints (TFR, change from baseline to week 24 in pain and fatigue) will be summarized by the following subgroups:

- NMO/NMOSD and AQP4 Status at screening (5 categories: NMO, NMOSD, NMO and AQP4 positive, NMO and AQP4 negative, and NMO/NMOSD and AQP4 positive)
- Geographical region (Asia, Others).
- Prior therapy for prevention of NMO/NMOSD attack (B-cell depleting therapy or immunosuppressants/others)
- Most recent attack in the last one year prior to screening (first attack or relapse).
- ADA status (ADA negative subjects, ADA unaffected subjects, Treatment-boosted ADA subjects, Treatment-induced ADA subjects) (see Section 4.13)

4.10.1.6 EQ-5D Scoring Algorithm

The EQ-5D 3 level version (EQ-5D 3L) descriptive system comprises the following 5 dimensions: mobility, self-care, usual activities, pain/discomfort, and anxiety/depression. Each dimension has 3 levels: no problem, some problems, and extreme problems. The

TP-GDO-WW-016-01 Confidential Version 7.0 Effective Date: 28Aug13 Version Date: 28NOV2018

Related to: SOP-GDO-WW-019 Page 18 of 60

scoring algorithm (US) as described in appendix 7.2 will be used but other norms may be explored for sensitivity analysis.

The EQ-5D index score will be missing in case any answer to one of the five EQ-5D dimensions is missing.

The EQ VAS records the respondent's self-rated health on a vertical, visual analogue scale ranging from 0 to 100 where the endpoints are labelled 'Best imaginable health state' and 'Worst imaginable health state'.

4.10.1.7 SF-36 Scoring Algorithm

The SF-36 is a multi-purpose, short form health survey with 36 questions. It yields an 8-scale profile (vitality, physical functioning, bodily pain, general health, role-physical, role-emotional, social role functioning and mental health) of functional health and well-being scores as well as psychometrically based physical and mental health summary measures and a preference based health utility index.

The SF36 will be scored using the Quality Metric proprietary scoring system (version 4.5). Component and domain scores are transformed to a 0-100 scale based on the 2009 US Normative population. Higher scores are indicative of better health related quality of life and a score of 50 is average for the US population.

For the SF-36, missing data rules will be applied according to the proprietary scoring software provided by the license holder (Maruish et al. 2011 p57 and p60).

4.10.1.8 FACIT-Fatigue Scale Scoring Algorithm

The FACIT Fatigue scale is a 13-item questionnaire that assesses self-reported fatigue and its impact upon daily activities and function over the past 7 days. As each of the 13 items of the scale ranges from 0-4, the range of possible scores is 0-52, with 0 being the worst possible score and 52 the best. Items are scored as follows: 0 = Not at all; 1= A little bit; 2= Somewhat; 3= Quite a bit; 4= Very much. All items are reverse scored except item An5 (*I have energy*) and An7 (*I am able to do my usual activities*). See Table 5-1 for further guidance.

When there are missing data, a total score is prorated from the score of the answered items, as long as more than 50% of the items are answered (i.e. a minimum of 7 of 13 items). The prorated score is calculated as the average of the non-missing scores multiplied by 13.

Table 5-1: FACIT scoring

Item code	Reverse iter	n Item response	Item score
HI7	4 -		
HI12	4 -	=	
An1	4 -		
An2	4 -	=	
An3	4 -	=	
An4	4 -	=	
An5	0 +		
An7	0 +	=	

TP-GDO-WW-016-01 Effective Date: 28Aug13 Related to: SOP-GDO-WW-019 Confidential Version 7.0 Version Date: 28NOV2018

Page 19 of 60

An8	4	_ =	
An12	4	- =	
An14	4		
An15	4	_ =	
An16	4	_ =	
		Sum individual item scores:	
		Multiply by 13:	
		Divide by number of items answered:	=FACIT
		score	

4.10.1.9 **EDSS Scoring**

The EDSS is an ordinal clinical rating scale ranging from 0 (normal neurological exam) to 10 (death due to NMO) in 0.5 unit increments that represent higher levels of disability. The EDSS scoring will be based on the score recorded on CRF.

4.10.1.10 mRS Scoring

The mRS is a 7-point disability scale that assesses the degree of disability in patients with neurological impairment. Possible scores range from 0 (no symptom at all) up to 6 (death). The higher scores reflect increased disability. The mRS scoring will be based on the score recorded on CRF

4.10.1.11 **ZBI Scoring**

The ZBI is the measurement to assess caregiver burden. The 22 items ask for the strain caregivers perceive. Responses range from 0 (never) to 4 (nearly always) with maximum score of 88. The higher the total score, the heavier the perceived burden. The ZBI scoring will be based on the score recorded on CRF. For summary tables, only questionnaire with responses to 17 or more out of 22 questions (\geq = 75% valid response) are used.

The ZBI can be scored if 17 or more items are completed. Interpretation approach can be used if at least 75% of the items have been completed:

- Sum the items that were answered.
- Divide the sum by the number of items that were answered to yield the mean response per item.
- Multiply the mean response per item by 22 (the total items in the scale).

4 10 1 12 Visual acuity function (Snellen chart)

Visual acuity will be measured by a Snellen 20-foot wall chart. The test will be performed monocularly and subjects may use their habitual distance glasses or contact lenses. If visual acuity is less than 20/200, these data will be recorded on CRF as below:

- If the subject can count fingers, this is recorded as "20/300" (CF).
- If the subject can see finger movements, this is recorded as "20/400" (HM).
- If the subject can perceive the flashlight, this is recorded as "20/500" (LP).
- If the subject cannot perceive the flashlight, this is recorded as "20/600" (NLP).

TP-GDO-WW-016-01 Confidential Version 7.0 Effective Date: 28Aug13 Version Date: 28NOV2018 Related to: SOP-GDO-WW-019

Page 20 of 60

In order to calculate change from baseline, visual acuity scores will be converted to logMAR visual acuity scoring. Transformation of scores will be conducted based on the following table (Table 5-2). If the record of visual acuity score (Snellen chart) is worse than 20/200 (i.e. CF, HM, LP or NLP in this study), the score will be converted to logMAR 1.85, logMAR 2.00, logMAR 2.70 and logMAR 3.00, respectively. If a score which is not in the table is recorded, it would be adjusted to the following lower score (e.g. 20/27 will be converted to 20/30).

Table 5-2: logMAR visual acuity scoring

Snellen chart	LogMAR
20/10	-0.30
20/12.5	-0.20
20/15	-0.12
20/16	-0.10
20/20	0.00
20/25	0.10
20/30	0.18
20/32	0.20
20/40	0.30
20/50	0.40
20/60	0.48
20/63	0.50
20/70	0.54
20/80	0.60
20/100	0.70
20/114	0.76
20/125	0.80
20/150	0.88
20/160	0.90
20/200	1.00
CF	1.85
HM	2.00
LP	2.70
NLP	3.00

4.10.2 Primary Efficacy Variable

The primary efficacy analyses will be based on the ITT population. Supportive evaluations will be performed using the PPS population.

The primary efficacy endpoint is TFR based on protocol-defined relapses confirmed by the CEC with EDSS/FSS assessment performed by the examining assessor within 7 days after relapse symptoms were reported to the site by the subject. TFR is defined as the time from the date of the randomization until the first occurrence of relapse throughout the double-blind period. Time point of relapse onset is defined as time at which the subject

TP-GDO-WW-016-01 Confidential Effective Date: 28Aug13 Version Date: 28NOV2018 Related to: SOP-GDO-WW-019

Version 7.0

experiences any new or worsening neurological NMO/NMOSD symptoms representing clinical relapse(s) which is later confirmed by the CEC as protocol-defined.

Patients will be censored at the end of double blind period for efficacy analysis (see section 4.2).

The primary analysis of the study is to test the equality of the TFR distribution between the SA237 and Placebo arms:

$$H_0$$
: TFR_{SA237} = TFR_{placebo} versus H_1 : TFR_{SA237} \neq TFR_{placebo}

A stratified log-rank test using strata of prior therapy for prevention of NMO/NMOSD attack (B-cell depleting therapy or immunosuppressants/others) and the most recent attack in the last year prior to baseline (first attack or relapse) will be used.

The Kaplan-Meier method will be used to estimate the TFR based on protocol-defined relapse distribution for each treatment group. The Kaplan-Meier curve will provide a visual description of the differences across treatment groups. In addition, estimates of the treatment effect will be expressed as hazard ratio and 95% confidence intervals using a Cox proportional-hazards model (Exact method will be used for tie data). The model will be stratified by prior therapy for prevention of NMO/NMOSD attack (B-cell depleting therapy or immunosuppressants/others) and the most recent attack in the last one year prior to screening (first attack or relapse). Treatment by covariate interactions will be assessed by including the pairwise interaction terms in the Cox proportional-hazards model.

The following summary tables, figures and analyses will be provided for the ITT and PPS:

- A summary table of Kaplan-Meier estimate of TFR (protocol-defined relapse) will be presented by treatment group.
- A figure of Kaplan-Meier estimate of TFR (protocol-defined relapse) will be presented by treatment group.
- Analysis of TFR (protocol-defined relapse) will be performed using stratified log-rank test.
- Analysis of TFR (protocol-defined relapse) will be performed using stratified Cox regression.

TFR (protocol-defined relapse) will be presented for the subgroups defined in section 4.10.1.5.

Additionally, sensitivity analyses of TFR (protocol-defined relapse) using a weighted stratified log-rank test, TFR (clinical relapse), TFR (treated clinical relapse), TFR (treated clinical relapse: optic neuritis), and protocol-defined relapse based on CEC adjudication (regardless of assessment limit of 7 days) will be conducted for ITT as follows For all sensitivity analyses, the same strata as for the primary endpoint will be used.

TFR (protocol-defined relapse) using a weighted stratified log-rank test: The sample size assumptions include a delayed treatment effect (see section 4.14). The influence of a

TP-GDO-WW-016-01 Confidential Version 7.0
Effective Date: 28Aug13 Version Date: 28NOV2018
Related to: SOP-GDO-WW-019 Page 22 of 60

potential delayed treatment effect will be assessed by using a weighted log-rank test using Fleming-Harrington weight function. Treatment effect is estimated adjusting for a change in the hazard ratio over time (i.e. non-proportional hazards). Based on simulations using blinded SA309 data, the parameters of the weight function are set to be rho=0 and gamma=1 (Lee 2007).

Clinical relapses: All relapses reported by investigators will be handled as events for TFR

Treated clinical relapses: Relapses treated with rescue therapy will be handled as events

Treated clinical relapse: optic neuritis: Relapses treated with rescue therapy and judged as optic neuritis by the investigator will be handled as events.

Optic neuritis will be identified via relapse assessment form before data base lock (for details see appendix 7.3). The same censoring rules as for the primary endpoint will be applied, except for the specific event of interest.

TFR (protocol-defined relapse) censored by affecting medications: Censored at the first timing of the start date of following medications:

- 1. Relapse prevention therapy
- 2. Rescue therapy
- 3. Systemic administration of steroid for other indication for more than 5 days
- A summary table of Kaplan-Meier estimate of TFR (clinical relapse) will be presented by treatment arm.
- A summary table of Kaplan-Meier estimate of TFR (treated clinical relapse) will be presented by treatment arm.
- A summary table of Kaplan-Meier estimate of TFR (treated clinical relapse: optic neuritis) will be presented by treatment arm.
- A summary table of Kaplan-Meier estimate of TFR (protocol-defined relapse based on CEC adjudication, regardless of assessment limit of 7 days) will be presented by treatment arm.
- A summary table of Kaplan-Meier estimate of TFR (protocol-defined relapse) censored by affecting medications will be presented by treatment group.
- A figure of Kaplan-Meier estimate of TFR (clinical relapse) will be presented by treatment group.
- A figure of Kaplan-Meier estimate of TFR (treated clinical relapse) will be presented by treatment group.
- A figure of Kaplan-Meier estimate of TFR (treated clinical relapse: optic neuritis) will be presented by treatment group.

TP-GDO-WW-016-01 Effective Date: 28Aug13 Related to: SOP-GDO-WW-019

- A figure of Kaplan-Meier estimate of TFR (protocol-defined relapse based on CEC adjudication, regardless of assessment limit of 7 days) will be presented by treatment group.
- A figure of Kaplan-Meier estimate of TFR (protocol-defined relapse) censored by affecting medications will be presented by treatment group.
- Analysis of TFR (protocol-defined relapse) will be performed using a weighted stratified log-rank test and the parameters of the weight function are set to be rho=0 and gamma=1.
- Analysis of TFR (clinical relapse) will be performed using stratified log-rank test.
- Analysis of TFR (treated clinical relapse) will be performed using stratified log-rank test.
- Analysis of TFR (treated clinical relapse: optic neuritis) will be performed using stratified log-rank test.
- Analysis of TFR (protocol-defined relapse based on CEC adjudication (regardless of assessment limit of 7 days)) will be performed using stratified log-rank test.
- Analysis of TFR (protocol-defined relapse) censored by affecting medications will be performed using stratified log-rank test.
- Analysis of TFR (clinical relapse) will be performed using the stratified Cox regression.
- Analysis of TFR (treated clinical relapse) will be performed using the stratified Cox regression.
- Analysis of TFR (treated clinical relapse: optic neuritis) will be performed using the stratified Cox regression.
- Analysis of TFR (protocol-defined relapse based on CEC adjudication (regardless of assessment limit of 7 days)) will be performed using the stratified Cox regression.
- Analysis of TFR (protocol-defined relapse) censored by affecting medications will be performed using stratified Cox regression.
- A by-subject listing of TFR, which also includes clinical relapse, treated clinical relapses and treated clinical relapse: optic neuritis, will be provided.

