4.3.2.1 Satralizumab and Placebo: Double-blind period

The patient will receive an SC injection of satralizumab or placebo at Weeks 0, 2 and 4, and Q4W thereafter during the double-blind period. The double-blind period ends when either the patient has a protocol-defined relapse which is adjudicated by CEC, the total number of registered relapses is 44 or 1.5 years after the date of randomization of the last patient enrolled, whichever comes first.

Patients who experienced a relapse during the double-blind period should continue the double-blind period regardless of rescue therapy unless the patient experiences a relapse which is adjudicated by CEC as a protocol-defined relapse, and will continue administration of study treatment at the discretion of the Investigator.

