3 INVESTIGATIONAL PLAN

3.1 Overall Study Design and Plan

This is a multicenter randomized, double-blind, placebo-controlled parallel assignment study followed by an open-label extension (OLE) period. Patients will be randomized to two groups (2:1, Group A or B) and will receive subcutaneous (SC) SA237 (Group A) or placebo (Group B) at Weeks 0, 2, 4, and every 4 weeks (Q4W) thereafter. The randomization will be stratified by prior therapy for prevention of NMO/NMOSD attack (B-cell depleting therapy or immunosuppressants/others) and the most recent attack in the last one year prior to screening (first attack or relapse). If a patient was administered B-cell depleting therapies (e.g. anti-CD20 antibody [e.g. rituximab], anti-CD19 antibody) at least once in the year prior to baseline, the patient will be stratified into "B-cell depleting therapy group" and otherwise into the "immunosuppressants/others group" (e.g. oral corticosteroids, azathioprine, mycophenolate mofetil, cyclosporine, methotrexate, tacrolimus).

Patients who experience a protocol-defined relapse which is adjudicated by the Clinical Endpoint Committee (CEC) in the double-blind period or complete the double-blind period can enter the open-label extension period. The double-blind period of the study ends when the total number of CEC-confirmed protocol-defined relapses is 44. At the end of the double-blind period, the clinical cut-off date for the primary analysis will be on the day of the onset of the protocol defined 44th relapse (adjudicated by the CEC) or 1.5 years after the date of randomization of the last patient enrolled, whichever comes first. In the extension period, patients can receive open-label treatment with 120 mg SA237 SC at Weeks 0, 2, 4, and every 4 weeks (Q4W) thereafter, until commercial availability of SA237 or Sponsor's decision to discontinue the development program.

For patients who experience a relapse in the double-blind period, appropriate rescue therapy for relapse will be administered. For patients who experienced a relapse which is adjudicated by the CEC as a protocol-defined relapse, SA237 should start under stable disease conditions (i.e. Day 31 or later, where Day 1 is defined as the day of onset of a protocol-defined relapse confirmed by CEC). For patients who completed the double-blind

TP-GDO-WW-016-01 Confidential Version 7.0 Effective Date: 28Aug13 Version Date: 28NOV2018

[figure not shown]
Related to: SOP-GDO-WW-019 Page 8 of 60

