4.2 General Presentation Considerations

The analyses periods are defined as follows:

- Study duration of double blind period for efficacy analysis
 - Study duration of double-blind period starts on the day of the randomization. The double-blind period ends on the earliest day of 1) clinical cutoff date (CCOD), 2) the day before the first treatment in the extension period, 3) the end of the study, or 4) last contact for patients lost to follow up.
- Double blind period for safety analysis
 - Double blind period starts on the day of first dose of study drug. The double-blind period ends on the same day as the efficacy analysis.
- Study duration of SA237 exposure for safety analysis (for All SA237 analysis)
 - Study duration of SA237 exposure starts on the day of first dose of SA237. Study duration of SA237 exposure ends on the earliest day of 1) CCOD, 2) the end of the study, or 3) last contact for patients lost to follow up.

The definition of summaries by visit is as follows:

- Summaries by visit for double blind period
 - Baseline is defined as the latest data before or on the date prior to first administration with either placebo or SA237. Summarized visits except for baseline are defined as follows. Irregular visits such as unscheduled visit between week X, dose outside the visit window (DOW), extra visit at relapsing, and the end of the study are out of scope. Week X visits are

TP-GDO-WW-016-01 Confidential Version 7.0 Effective Date: 28Aug13 Version Date: 28NOV2018

Related to: SOP-GDO-WW-019

Related to: SOP-GDO-WW-019

directly used for categories of time. In other words, time window is not applied. If there are the same visits data, one representative assessment nearest to the scheduled visit day will be summarized.

- Summaries by visit for All SA237 analysis
 - Baseline is defined as the latest data before or on the date prior to first administration of SA237. Summarized visits except for baseline are defined as follows. Irregular visits such as unscheduled visit between week X, dose outside the visit window (DOW), extra visit at relapsing, and the end of the study are out of scope. Time window is applied as if visit schedules continue in the double-blind period. Middle of each specified day of visit will be used for the range of time window of each visit. One representative assessment nearest to the specified day of visit in time window of each visit will be summarized

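### The Kaplan-Meier table for treated optic-neuritis relapse overstates the share of patients who have one in the double-blind period, by more points on placebo than on satralizumab

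*SAP*

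**What the plan says.** SAP 4.10.2 lists treated optic-neuritis relapse among the sensitivity analyses of the primary endpoint. The event definition is: "Relapses treated with rescue therapy and judged as optic neuritis by the investigator will be handled as events". On censoring it says: "The same censoring rules as for the primary endpoint will be applied, except for the specific event of interest". The output is: "A summary table of Kaplan-Meier estimate of TFR (treated clinical relapse: optic neuritis) will be presented by treatment arm". A matching figure, a stratified log-rank test and a stratified Cox model are also planned.

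The primary rule censors at the end of the double-blind period as defined in SAP 4.2, which is the earliest of four dates. For a patient who moves on, the operative one is "2) the day before the first treatment in the extension period".

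A confirmed relapse at any site opens the way to the extension. Protocol 4.3.2.1: "The double-blind period ends when either the patient has a protocol-defined relapse which is adjudicated by CEC". SAP 3.1 sets the earliest start of extension treatment at "Day 31 or later, where Day 1 is defined as the day of onset of a protocol-defined relapse confirmed by CEC". Entry is optional (Protocol 4.3.2.2). A relapse that the CEC does not confirm does not cause exit: under Protocol 4.3.2.1 such patients "should continue the double-blind period regardless of rescue therapy unless the patient experiences a relapse which is adjudicated by CEC" as protocol-defined.

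Neither document plans a cumulative incidence function, names a competing event, or states which risk the optic-neuritis curve is meant to estimate.

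**The concern.** In the primary analysis a protocol-defined relapse at any site is the event, so leaving after one causes no difficulty. The optic-neuritis analysis narrows the event but keeps the censoring rule. A patient with confirmed myelitis who enters the extension now counts as a censored observation, and Kaplan-Meier treats that patient as still facing the same optic-neuritis risk as those who stay on blinded treatment. In fact the patient left because of the disease under study and, if on placebo, has switched to active drug.

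The overstatement grows with the hazard of other relapses. It is therefore larger on placebo, and it widens the apparent absolute benefit. The table and figure are where a reader would look for the absolute risk of optic neuritis.

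**Working it through.** **Inputs** (Protocol 6.2, SAP 4.14): placebo hazard 1.1295 per year; hazard ratio 1.0 for 2 months, then 0.25; 90 patients randomized 2:1, so 30 on placebo; 33 months of accrual plus 5 of follow-up; 10% dropout over 2 years, which is -ln(0.9)/2 = 0.0527 per year. The optic-neuritis share p of relapses is not in the documents. I assume 0.40, range 0.30-0.50, equal in both arms and constant over time.

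**The plan's own figures.** The mean rate is 0.7 × 1.5 + 0.3 × 1.0 = 1.35. The Gamma-Poisson zero probability with variance/mean √2 is (√2)^(-1.35/(√2-1)) = 0.3232, and -ln(0.3232) = 1.1295, as stated. In simulation, 44 events give 81.3% power with linearly rising accrual (44.1 events expected by month 38) and about 84% with uniform accrual (50.3 expected). The accrual shape is not stated.

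**Week 48, upper bound** (exit at relapse onset, every non-optic relapse causes exit), t = 48/52 = 0.923 years:

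- Cumulative hazard H, placebo: 1.1295 × 0.923 = 1.043.
- H, satralizumab: 1.1295 × 2/12 + 0.2824 × (0.923 - 0.167) = 0.402.
- One minus Kaplan-Meier = 1 - exp(-pH). Cumulative incidence = p(1 - exp(-H)).

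| p | Placebo: 1-KM / cumulative incidence | Satralizumab: 1-KM / cumulative incidence | Risk difference: 1-KM / cumulative incidence |
|---|---|---|---|
| 0.30 | 26.9% / 19.4% | 11.4% / 9.9% | 15.5 / 9.5 |
| 0.40 | 34.1% / 25.9% | 14.8% / 13.2% | 19.2 / 12.7 |
| 0.50 | 40.6% / 32.4% | 18.2% / 16.5% | 22.4 / 15.8 |

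At p = 0.40 the excess is 8.2 points on placebo and 1.6 on satralizumab.

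**Lag and incomplete exit.** Let L be the lag from relapse onset to the extension dose and q the fraction of non-optic relapses that lead to exit. On placebo, with λ = 1.1295 and a = p + q(1 - p), cumulative incidence = 1 - exp(-pλL) + (p/a) exp(-pλL)[1 - exp(-aλ(t - L))]. With L = 31/365.25 = 0.0849, exp(-pλL) = 0.9624.

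- q = 1: 0.0376 + 0.40 × 0.9624 × (1 - 0.3880) = 27.3%. Excess 34.1 - 27.3 = 6.8 points.
- q = 0.5 (a = 0.7): 0.0376 + 0.5714 × 0.9624 × (1 - 0.5154) = 30.4%. Excess 34.1 - 30.4 = 3.7 points.

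For satralizumab, simulation gives an excess of 1.2 and 0.6 points in the same two cases.

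**How far out the curve can be read.** Expected placebo patients at risk = 30 × P(no relapse) × P(not dropped out) × P(followed that long). This uses zero lag and full exit.

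- Week 48: 30 × 0.353 × 0.953 × 0.816 = 8.2 with uniform accrual. With rising accrual the last factor is 0.666, giving 6.7.
- Week 96 (t = 1.846): 30 × 0.124 × 0.907 × 0.480 = 1.6 with uniform accrual. With rising accrual the last factor is 0.231, giving 0.8.

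A 31-day lag changes these little: 7-9 patients at Week 48 and about 1-2 at Week 96.

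**The case against.** The strongest reply is that this is a choice of target. A non-optic relapse does not make optic neuritis impossible; it ends blinded observation. Kaplan-Meier aims at the risk had nobody left. Cumulative incidence gives the risk before leaving, which is lower on placebo partly because the design removes placebo patients sooner. The SAP never says its curve is a share of patients. This stands, so Kaplan-Meier should not be called simply wrong. But its hypothetical target needs exit to be independent of optic-neuritis risk, which the data cannot verify, and the SAP states neither target nor assumption.

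The model is also rough. The hazard is for CEC-confirmed relapse, while the event is an investigator-judged treated relapse. SAP Appendix 7.3 does not require isolated optic neuritis, so mixed relapses count as events. These points bear on the size and are why the tabulated figures are upper bounds given the assumed share; they do not reverse the direction.

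A reader might go to Week 96, where the same model gives 57% against 35% on placebo and a risk difference of 33 points instead of 16. The documents do not support leading with that: only about 1-2 placebo patients would remain at risk, and the SAP commits to no Week 96 optic-neuritis risk.

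Finally, this is one sensitivity analysis, outside the testing hierarchy in SAP 4.10.1.4, and a by-subject listing is planned. That limits the consequence but does not correct the table.

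**Conclusion.** The point holds for the absolute risks in one table and one figure. One minus Kaplan-Meier overstates the double-blind share with a treated optic-neuritis relapse. At Week 48 and a 40% share, the excess is at most about 8 points on placebo and 1.6 on satralizumab. It is about 7 and 1.2 with a 31-day lag, and about 4 and 0.6 if only half of non-optic relapses also lead to exit. The imbalance is clearest in points; as a ratio at one year, with zero lag and full exit, it is milder, 1.34-fold on placebo against 1.13-fold on satralizumab. The size rests on the planning hazards and on a share the documents do not give.

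A reader might infer that the treatment comparison for optic neuritis, or the primary result, is biased. It is not, on this ground: the log-rank and Cox analyses compare cause-specific hazards, and the primary endpoint counts protocol-defined relapses at every site.

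**What to change.** In SAP 4.10.2, for treated optic-neuritis relapse, add Aalen-Johansen cumulative incidence by arm, with exit to the extension after a non-optic protocol-defined relapse as the competing event. Take any stated absolute risk or risk difference from it. If the Kaplan-Meier table and figure stay beside it, label them as a hypothetical risk that assumes exit is independent of optic-neuritis risk. Keep the stratified log-rank and Cox analyses and label them cause-specific.

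No new data are needed. The cost is one more table and figure, and smaller reported absolute risks and a smaller risk difference.
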